From each of these geographically-stratified study sites, 32 green intervention homes and 32 control homes (total = 64 homes * 13 study sites = 832 homes) will be included. Within each study site (i.e., city), both the green intervention and control homes will be from the same housing development or neighborhoods to ensure homogeneity with regard to housing type and other socioeconomic factors. Changes in environmental measurements (pesticides, VOCs, particulate matter (i.e., PM 2.5 and 1.0), indoor allergens, and fungi) over the 1-year follow-up in both types of housing (green intervention and control) will be compared, thus each home's follow-up measurements will be compared with its own baseline exposure level. This two-group pre-post within-group and between-group comparison will increase ability to detect differences in exposure levels and asthma outcomes that might result from the green renovations in our study. In addition, we will compare environmental measurements and health outcome data with national surveillance data (i.e., National Health and Nutrition Examination Survey (NHANES) and the National Lead and Allergen survey) or other relevant populations (e.g., National Cooperative Inner City Asthma Study (NCICAS), Inner City Asthma Study (ICAS)). At this time, these sites have not been determined by HUD and CDC. When the study sites are selected, the data collection partners will include: 1) CDC; 2) HUD, and 3) the contracted research institutions (to be determined).

An overview of the study implementation is described below. Briefly, study sites will be selected, participants will be recruited at each study site, survey, clinical, and environmental sample collection will occur at repeated time points, samples will be analyzed in selected laboratories, statistical analysis will be conducted, and results will be translated to participants and the community in general. All study consent forms and questionnaires will be available in both English and Spanish (by certified translators). Reading level will be maintained at an 8th grade level (Flesh-Kinkaid assessment available through Microsoft Word).

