(based on Tuomainen et al, 2003)			
Piperonyl butoxide			
0.8 ng/m^3 decrease	3.6	0.33	418
(based on Williams et al, 2006)			

* $\alpha = 0.05$, $1-\beta = 0.80$

Summary of samples size for environmental exposures: Of the intervention studies relevant to green housing, the sample size calculations based upon the cockroach allergen intervention study provided the most information to inform our estimates of sample size required for the Green Housing Study. Because [name] was a co-author on the manuscript and had analyzed the cockroach allergen samples in her laboratory, she had

access to the repeated measurements database and this helped to guide our design effect due to clustering of apartments within buildings. The other papers did not have repeated measurements (thus the variance estimates were rather wide) and they also had more restrictive groups (e.g., nonsmoking pregnant women, Finnish families living in newly-constructed apartments) than is planned in the Green Housing Study. Thus, we believe that our conservative estimate to recruit residents in 64 apartments in each of 13 cities (total n= 832 homes) to account for potential loss-to-follow-up, should ensure adequate sample size for assessing differences in exposure levels.

Sample size for assessing asthma outcomes: The calculation for assessing differences in health markers were based upon a multi-site asthma intervention study (Morgan et al. 2004). In this study, 407 asthmatic children with the multi-factorial intervention (asthma trigger education, mattress covers, IPM, HEPA filter units) had fewer days (2.62 days ± 0.12) than those (n=414) without the intervention (3.21 days ± 0.13). Table 10 shows sample sizes with different assumptions of effect sizes using equation 2.

Equation 2. Sample size for asthma morbidity outcomes.

$$m = D * [2(z_{\alpha} + z_{\beta})^2 \{1 + (n - 1)\rho\}] / (n\Delta^2)$$

m = number in each group (e.g., intervention and non-intervention)

n = 1 (note: for differences of differences, we assumed a value of 1)

z_{α} = Z score for alpha = 0.05

z_{β} = Power, set at 0.80

ρ = correlation among repeated observations

Δ = d/ σ where d is the smallest meaningful difference and σ is the standard deviation

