D = Design effect due to clustering (This was not in the formula used by Diggle et al. 1994, but was added to adjust for clustering expected in our study). Based upon the Kwon et al paper (2003) that showed a design effect of 1.5 was helpful for designing cluster studies to assess asthma outcomes in national surveys (e.g., BRFSS and NHANES), we assumed a slightly smaller design effect equal 1.2 due to the expected low number of expected of average children per cluster).

Summary of sample size for asthma outcomes: Based upon both the Morgan et al. (2004) and Krieger et al (2005) studies, a sample size of at least n=274 in each group (Green intervention vs. non-intervention) should provide 80% power to detect differences in asthma outcomes such as symptom-days and urgent care visits. As mentioned in the summary above, we will enroll the children from 832 homes in order to ensure adequate power to detect both the asthma and exposure outcomes.

Main Variable Definitions

Type of rehabilitation: The main variable of interest is the type of home (green vs. control); however, within each type, there are different permutations. For example, HUD has two levels of green which are based upon the acceptance of HUD-approved recommendations: Level 1) landlord agrees to implement at least 75% of the dollar amount of green repairs and improvements; and Level 2) landlord agrees to implement at least 50% of the dollar amount. While discretizing the green rehabilitation into Level 1 and Level 2 categories could simplify our analysis, we acknowledge that the two different levels do not necessarily capture green materials or practices that are potentially related to health. For example, a green home could have low VOC paint, or low VOC carpet, or replace the kitchen cabinets with low VOC materials, or have some combination of these activities. A control home may also include some green materials (such as low flow toilets or EnergyStar appliances)—the distinction here is that a control home is not required to use green materials or practices. Therefore, we will attempt to isolate the main effects of specific background variables such as low VOC paint, low VOC carpet, and kitchen cabinet replacement.

Allergens in the homes: Variables related to dust mite (Der p 1 and Der f 1), cockroach (Bla g 2), cat (Fel d 1), and mouse (Mus m 1) allergen in the homes may take the form of continuous measures of specific allergens or

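### The 274 children per group is labelled a difference-of-differences calculation but sizes a comparison of one value per child, so its 80% power is not established for the pre-post contrast

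*Protocol*

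**What the plan says.** Protocol section IV.d, under the heading on sample size for asthma outcomes, takes its symptom-day inputs from a multi-site asthma intervention study. The 407 children who received that intervention "had fewer days (2.62 days ± 0.12) than those (n=414) without the intervention (3.21 days ± 0.13").

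Equation 2 is m = D · 2(z_α + z_β)²{1 + (n − 1)ρ} / (nΔ²). Its terms are defined as follows:

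- "n = 1 (note: for differences of differences, we assumed a value of 1")
- "z_{α} = Z score for alpha = 0.05", with one- or two-sided not stated
- "z_{β} = Power, set at 0.80"
- "ρ = correlation among repeated observations", with no value given for symptom-days
- "Δ = d/ σ where d is the smallest meaningful difference and σ is the standard deviation", without saying whether this is the SD of a level or of a change
- a design effect D of 1.2

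Table 10 prints 274 per group at an effect size of 0.232, footnoted as the effect observed in that study. The summary that follows says that "a sample size of at least n=274 in each group (Green intervention vs. non-intervention) should provide 80% power" for outcomes such as symptom-days.

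Section IV.a (Overview) describes a two-group pre-post comparison, within and between groups, and says that it "will increase ability to detect differences in exposure levels and asthma outcomes".

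**The concern.** A difference of differences compares the two groups on each child's change from baseline. The variance of a change depends on the correlation between the baseline and follow-up values. Setting n = 1 removes the correlation from Equation 2, which is legitimate for a change score only if σ is already the SD of the change. The means in the protocol are group levels, so σ appears to be the SD of the level. If so, the 80% power belongs to a different statistic from the one that the note names, and the number on which the asthma aim relies has no stated link to the planned pre-post contrast.

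**Working it through.** **1. Reproduce the printed figure.** Inputs are from section IV.d. Reading the ± values as standard errors:

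- SDs: 0.12 × √407 = 2.421 and 0.13 × √414 = 2.645, pooled 2.536
- d = 3.21 − 2.62 = 0.59
- Δ = 0.59 / 2.536 = 0.2326, which is Table 10's 0.232

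With n = 1, the term {1 + (n − 1)ρ}/n equals 1, so m = 2D(z_α + z_β)²/Δ²:

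- one-sided alpha 0.05: 1.2 × 2 × (1.645 + 0.842)² / 0.2326² = 274.2, the printed 274
- two-sided alpha 0.05: 348.1, which does not match

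So 274 contains the SD of a level, one value per child, no correlation and a one-sided alpha.

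**2. Put in the variance of a change score.** For one baseline and one follow-up with equal SDs, Var(change) = 2(1 − ρ)σ². The requirement in step 1 is multiplied by 2(1 − ρ), a factor that equals 1 only at ρ = 0.5. Power is Φ(Δ√{m / [2D · 2(1 − ρ)]} − z_α). The 0.59 is kept as the difference in mean change, which assumes equal baseline means. The protocol gives no ρ for symptom-days, so the range is assumed. Required numbers are rounded up.

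| ρ | Needed, one-sided | Power at 274 | Power at 333 | Needed, two-sided | Power at 274 | Power at 333 |
|---|---|---|---|---|---|---|
| 0.2 | 439 | 63% | 70% | 558 | 50% | 58% |
| 0.3 | 384 | 68% | 75% | 488 | 56% | 64% |
| 0.4 | 330 | 73% | 80% | 418 | 62% | 71% |
| 0.5 | 275 (274.2) | 80% | 86% | 349 | 70% | 78% |
| 0.6 | 220 | 87% | 92% | 279 | 79% | 87% |

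The 333 is the planned enrolment less the stated 20% loss: 832 / 2 × 0.8 = 332.8.

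**3. Correlation at which the change score reaches 80% power.** ρ = 1 − m/(2 × 274.2) one-sided, or 1 − m/(2 × 348.1) two-sided:

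- at 274 per group: 0.50 one-sided, 0.61 two-sided
- at 333 per group: 0.39 one-sided, 0.52 two-sided

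**4. Other contrasts that the planned visits allow.**

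- *Follow-up adjusted for baseline*, factor 1 − ρ². One-sided, 274.2 × 0.96 = 263 at ρ = 0.2 and 274.2 × 0.91 = 250 at ρ = 0.3. The factor never exceeds 1, so this needs no minimum ρ relative to the level calculation. Two-sided, the numbers are 348.1 × 0.96 = 334 and 348.1 × 0.91 = 317.
- *Mean of the 6- and 12-month visits minus baseline*, factor 1.5(1 − ρ) if all visits are equally correlated. At ρ = 0.3 the factor is 1.05. One-sided this gives 288 per group and 85% power at 333. Two-sided it gives 366 per group and 76% power at 333. The thresholds at 274 are 0.33 one-sided and 0.475 two-sided.

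**5. Sidedness within Table 10.** The rows for 0.30, 0.35 and 0.40 print 206, 151 and 116. The formula gives 165, 121 and 93 one-sided, or 209, 154 and 118 two-sided, so these rows lie near the two-sided values while the 0.232 row fits only one-sided. Table 10 also prints 274 for an effect size of 0.20, where the formula gives 371 one-sided or 471 two-sided. That is a separate error.

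**The case against.** The strongest reply is that no passage commits the asthma analysis to an unadjusted change score. The regression paragraph in section IV.d plans models on the green-versus-control coefficient, and the plan for Hypothesis 2 speaks of odds or rate ratios for cumulative incidence. On that reading the note is a wrong label on a level calculation. This stands, and it limits the threshold in step 3 to one estimator.

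A reader might infer that the pre-post design lowers power whenever the correlation is below 0.5, and so that the Overview is wrong to say the design helps. The documents do not support that. Baseline data cost power only if they are used in an unadjusted change score. With baseline adjustment the requirement never exceeds that of the level calculation.

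A reader might also infer that the trial is underpowered for symptom-days. That is not shown either. The true correlation is unknown, and enrolment leaves about 333 per group rather than 274. The one correlation in the protocol, about 0.5, is for cockroach allergen in control homes. At that value the one-sided change-score requirement happens to equal 274, but it is no evidence about symptoms.

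Finally, the protocol neither labels the ± values as standard errors nor says whether the source means come from one visit or are averaged over follow-up. If they are averaged, the simple 2(1 − ρ) factor does not apply directly. The standard-error reading is supported by its reproducing 0.232. The averaging question cannot be settled from the protocol.

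None of this supplies the missing link. The note names differences of differences, and the inputs and formula are those of a level comparison.

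**Conclusion.** The point holds in this limited form: the 274 per group and its 80% power are not established for the pre-post contrast named in the Equation 2 note and the Overview. The size of any shortfall depends on the estimator, the sidedness of alpha and a correlation that the protocol does not give. For an unadjusted change score with one baseline and one follow-up, power at 274 is 68% at an assumed correlation of 0.3 one-sided, and 56% two-sided. For a baseline-adjusted comparison at one-sided alpha there is no shortfall. At two-sided alpha even the level calculation has only 70% power at 274 and 78% at 333, so sidedness matters as much as the choice of contrast.

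**What to change.** In Equation 2 and Table 10, remove the n = 1 note or replace it with the variance factor of the contrast to be used:

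- preferably the baseline-adjusted comparison of follow-up, m = 2D(z_α + z_β)²(1 − ρ²)/Δ²
- otherwise the change score, with 2(1 − ρ) in place of (1 − ρ²)
- or the mean of the 6- and 12-month visits minus baseline, with {1 + ρ}/2 + 1 − 2ρ

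State whether alpha is one- or two-sided and use the same convention in every row. State that σ is the SD of a level and that ± was read as a standard error. Give an assumed ρ for symptom-days with a range such as 0.2 to 0.6. Restate power at 274 and at the roughly 333 retained per group, and align the power sentence in the asthma summary. If a follow-up-only comparison is intended, dropping the label and saying so is enough for this point, with sidedness still to be stated.

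The cost is protocol wording and one recalculated table, with no extra children or visits. The stated power may come out less favourable, particularly at two-sided alpha.

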D = Design effect due to clustering (This was not in the formula used by Diggle et al. 1994, but was added to adjust for clustering expected in our study). Based upon the Kwon et al paper (2003) that showed a design effect of 1.5 was helpful for designing cluster studies to assess asthma outcomes in national surveys (e.g., BRFSS and NHANES), we assumed a slightly smaller design effect equal 1.2 due to the expected low number of expected of average children per cluster).

Summary of sample size for asthma outcomes: Based upon both the Morgan et al. (2004) and Krieger et al (2005) studies, a sample size of at least n=274 in each group (Green intervention vs. non-intervention) should provide 80% power to detect differences in asthma outcomes such as symptom-days and urgent care visits. As mentioned in the summary above, we will enroll the children from 832 homes in order to ensure adequate power to detect both the asthma and exposure outcomes.

Main Variable Definitions

Type of rehabilitation: The main variable of interest is the type of home (green vs. control); however, within each type, there are different permutations. For example, HUD has two levels of green which are based upon the acceptance of HUD-approved recommendations: Level 1) landlord agrees to implement at least 75% of the dollar amount of green repairs and improvements; and Level 2) landlord agrees to implement at least 50% of the dollar amount. While discretizing the green rehabilitation into Level 1 and Level 2 categories could simplify our analysis, we acknowledge that the two different levels do not necessarily capture green materials or practices that are potentially related to health. For example, a green home could have low VOC paint, or low VOC carpet, or replace the kitchen cabinets with low VOC materials, or have some combination of these activities. A control home may also include some green materials (such as low flow toilets or EnergyStar appliances)—the distinction here is that a control home is not required to use green materials or practices. Therefore, we will attempt to isolate the main effects of specific background variables such as low VOC paint, low VOC carpet, and kitchen cabinet replacement.

Allergens in the homes: Variables related to dust mite (Der p 1 and Der f 1), cockroach (Bla g 2), cat (Fel d 1), and mouse (Mus m 1) allergen in the homes may take the form of continuous measures of specific allergens or

of indicator variables for the presence or absence of certain allergens or combinations of allergens. Allergen concentrations will be reported as μg of allergen per g of collected dust and μg of allergen per unit area vacuumed.

VOCs and pesticides in the homes: Variables related to VOCs (whether total or speciated) and pesticides (pyrethroids, propoxur, and piperonyl butoxide) in the homes may take the form of continuous measures or indicator variables for the presence or absence of certain chemicals or combinations of chemicals. Concentrations will be reported as ppm (and also $\mu\text{g}/\text{m}^3$) in the case of the VOCs and $\mu\text{g}/\text{g}$ in the case of the pesticides.

Conditions of the home environments: Factors that may influence the presence and levels of allergens, VOCs, and pesticides include: the presence of carpets; pests; housing type and age, average winter temperature and relative humidity, air exchange rates.

Wheeze /asthma severity: This information may be used in the form of categorical and continuous variables (number of emergency room visits for asthma, use of asthma medications, lost school days). Nights awakened by asthma, and spirometry measurement such as FEV1 and FEF_{25-75%}).

Additional environmental and host factors for disposition to wheeze/asthma: Other risk factors for the main outcomes of interest include: environmental tobacco smoke; acute respiratory illnesses; gender; socioeconomic status of primary caregiver; degree of acculturation (operationalized); and deficiencies in access to and quality of health care. Many of these factors allow for a variety of formulations. Environmental tobacco smoke, for example, may be analyzed as an indicator variable for the presence or absence of smoking in the home, as count data for the number of smokers in the home, or as a continuous variable for the number of cigarettes smoked per day in the home. The choice of formulation of risk factors will be driven by the aim of clarifying the main relationships of interest, for example the role of allergens in the development of early allergic sensitization and asthmatic airways disorders.

In the case of dichotomous outcomes, multiple logistic regression will be used to calculate odds ratios (in the case of rare events such as overnight hospitalizations due to asthma attacks). When rare events exceed 10%, then risk ratios will be calculated from the logistic regression (J. Zhang & Yu, 1998). Hierarchical linear modeling will be used for evaluating effects of individual apartment, neighborhood and regional factors on levels of environmental agents. The main outcomes are allergen, VOC, and pesticide levels in the home; however, several factors should be adjusted in the analysis, including but not limited to smoking in the home, proximity to major roadways, and region of the country. For example, researchers in Baltimore found a low prevalence of both cockroach exposure and sensitization among children in high SES African American families (Sarpong, Hamilton, Eggleston, & Adkinson, 1996). This observation highlights a possible mechanism through which factors operating at the social/environmental level (e.g., deteriorated built environment) might contribute to asthma among disadvantaged urban children, i.e., via increased exposure indoor allergens (V.A. Rauh et al., 2002). Conceivably, the greenest of homes could still have poor indoor air quality due to some of the aforementioned factors.

The analytical plan for specific hypotheses are:

Hypothesis 1: Green housing will lead to 1) lower levels of environmental contaminants compared with those of control housing, and 2) lower levels of related biomarkers in the residents of green vs. control housing.

The longitudinal study here outlined will permit estimation of:

Geometric mean (GM) and standard deviation (GSD) for each of the environmental analytes (e.g., pesticides, VOCs, mold, and indoor allergens) by rehabilitation type (green vs. control).

Geometric mean (GM) and standard deviation (GSD) for each of the biomarkers for pesticides and VOCs by rehabilitation type (green vs. control).

Correlations between environmental measurements and biomarkers (stratified by several characteristics including but not limited to age and gender).

Proportion of green vs. control homes that have pesticides that are currently banned for residential use by EPA.

Hypothesis 2: If irritants and allergens are lower in green vs. control housing, residents of green housing should experience fewer and less severe asthma exacerbations.

The longitudinal study here outlined will permit estimation of:

Odds ratios (OR) or Rate Ratios (RR) for exposures to environmental agents and cumulative incidence of wheeze and/or other asthma-related morbidity measurements (among children ages 7-12 with asthma).

Odds ratios (OR) or Rate Ratios (RR) for exposures to environmental agents and cumulative incidence of wheeze and/or other asthma-related morbidity measurements (among mothers/ primary caregivers).

This analysis is also secondary; we expect that asthma among adults will be influenced by other factors unrelated to green housing (e.g., their own smoking habits, occupational exposures).

Missing data (e.g. loss to follow-up)

We anticipate the inevitable occurrence of missing data, including dropouts. First, if the missingness of the data is sufficiently small and the associations of interest are sufficiently large, the simple device of imputing upper and lower bound data, if possible, will suffice. That is, a small amount of missing data and a large effect size will allow a unique inference to stand no matter whether the missing data are imputed at their minimum or maximum possible values and used as such. This is consistent with the most conservative approaches adopted in clinical trials wherein subjects lost to follow-up are assumed to have died or to have otherwise suffered the worst possible endpoint. In general however, we must anticipate that we may be facing larger missingness and/or smaller effect sizes and/or impractical upper and lower bounds, such that primary inference changes

between the extremes. In this case we will use the multiple imputation procedure of Rubin (Rubin, 1985) to address the problem. In this technique, a fair amount of effort is devoted to the construction of an imputation model or set of models to provide best estimates of missing endpoints. These best estimates may include the best case or worst case scenarios; the point is that they should most fairly represent data that are missing given the observable information at hand. The imputation models may need to assume data missing at random or they may need further specification to allow for non-ignorable missingness. Each analysis must develop its own best imputation model for missing data, using available observed covariates and non-missing endpoints.

Database management system

All interview, environmental, and other data recorded on paper forms will be reviewed for coding problems and corrected prior to data entry. All records will be entered with range and logic checks and all discrepancies resolved with reference to the paper records. When possible, laboratory data will be downloaded from their respective software to computers in ASCII format in order to decrease data entry errors. Otherwise, biologic and environmental sample information will also be recorded on forms which mirror the computer screen in order to facilitate data entry. Chain of custody for biologic and environmental samples will be maintained at each study site and (de-identified data will be maintained at CDC). All data will undergo a series of quality control checks designed to detect missing data points and invalid datapoints, such as incorrect dates. All data will be converted to SAS format for analysis with participant number, visit type, and visit date used to link across computer and paper data files. At regular intervals, the data will be queried for routine descriptive statistics on all interview items, environmental measures, and clinical data. These will be scrutinized for patterns suggesting outliers, scoring errors, data entry errors, etc. Problems suggesting protocol deviations need for retraining, or similar issues will be resolved through meetings of the research team and field staff.

PCs running ACCESS software will be used for data management with original and working analytic data files backed up regularly to a password protected server on a local area network, which is itself backed up nightly. All paper records and removable computer disks containing confidential data generated during the study will be kept in locked file cabinets; all other electronic data will be maintained in password protected folders. Access to either will be limited to authorized staff. Survey instruments have been designed in Microsoft ACCESS®, which will facilitate data entry into this relational database. Biologic and environmental sample information will also be recorded on forms which mirror the computer screen in order to facilitate data entry. Chain of custody for biologic and environmental samples will be maintained at each study site. All data will undergo a series of quality control checks designed to detect missing data points and invalid datapoints, such as incorrect dates.

Confidentiality of the Data

Data from paper questionnaires will be entered by the contracted data collectors into a database (e.g. Microsoft Access) which will also be password-protected. Dates of birth and home addresses are primary direct identifiers and the contractor's removal of other direct identifiers (such as name, phone numbers, e-mail addresses) will minimize identification but not completely eliminate it. A unique Study ID will be assigned by the contractor as a key identifier for all study forms. The environmental and biological samples and measurements will only be identified by study ID. Contracted data collectors will maintain their paper files in locked cabinets and their electronic files will be stored on secured servers with password protection. Encrypted data files will be sent electronically to Green Housing Study investigators at CDC. Data will be stored on highly-secured CDC servers in Atlanta, GA. The servers are housed in a secure computer room complete with climate control, emergency power, and an uninterruptible power supply (UPS). Daily back-ups and integrated security are implemented through the CDC computer services infrastructure. All data access is password-protected, and all network communications use encryption. All servers and PCs that are part of the CDC infrastructure are protected by both host-based firewalls and software in order to prevent the undetected

installation of "spyware". Only Green Housing Study investigators at CDC will be given access to read the encrypted data files.

CDC Green Housing Study investigators will receive electronic files with date of birth, medical information, biological specimens, employment status, and home address identified by study ID number. If there were a breach of confidentiality for any of the above IIF, some effect on the respondent's privacy could occur; however, the screening form will be the only form that contains name, home address, phone number, e-mail address, and study ID together; only the contracted data collectors will have this form. The contracted data collectors will only use name, phone number, e-mail address, and home address for locating the study participant and ensuring that follow-up questionnaires and clinical and environmental measurements are repeated accordingly. Contracted data collectors will be required to have human subjects training in accordance with their institution's Institutional Review Board (IRB) and/or the CDC's IRB.

Quality Control and Quality Assurance

Training of study staff will occur centrally at CDC prior to beginning recruitment. The training will include lecture, demonstration, and practice components to insure that all staff are fully trained. Staff will complete certification to demonstrate acceptable levels of knowledge regarding each study component that they will be involved in performing.

The site PIs and study coordinators will be responsible for insuring that all procedures are performed according to the protocol. Periodic reviews of the procedures will be conducted by the study coordinator.

A Green Housing Study Manual of Procedures will be provided to all investigators and staff members. This manual will include detailed descriptions, including SOPs (standard operating procedures) and case report forms, for each study activity or procedure.

Representatives from the CDC will conduct site visits periodically to assess adherence to the protocol and progress of enrollment. Other areas of review will include data collection procedures, data entry, timeliness of form completion and data entry, and security measures for study data.

Ethics/Protection of Human Subjects

Institutional Review Board/Ethics Committee

Each participating institution must provide for the review and approval of this protocol and the associated informed consent documents by an appropriate ethics review committee or Institutional Review Board (IRB). Any amendments to the protocol or consent materials must also be approved before they are placed into use. Only institutions holding a current US Federal-Wide Assurance issued by the Office for Human Research Protections (OHRP) may participate.

Informed Consent Process

Informed consent is a process that is initiated prior to the individual's agreeing to participate in the study and continuing throughout the individual's study participation. Extensive discussion of risks and possible benefits of will be provided to the participants. Consent forms describing in detail the study procedures and risks will be given to the participant. Written documentation of informed consent is required prior to starting the study. Consent forms will be IRB-approved and the participant will be asked to read and review the document. Upon reviewing the document, the investigator will explain the research study to the participant and answer any questions that may arise. The participants should have sufficient opportunity to discuss the study and process the information in the consent process prior to agreeing to participate. Spanish- and Chinese-speaking participants will be provided with consent documents in Spanish or Chinese and the consent discussion will be facilitated or conducted by a bilingual (Spanish/English or Chinese/English) interviewer. The participants and their parents/guardians may withdraw consent at any time throughout the course of the study. A copy of the informed consent document will be given to the participants for their records. The rights and welfare of the

participants will be protected by emphasizing to them that the quality of their medical care or housing situation will not be adversely affected if they decline to participate in this study.

Assent Process

Study participants will be 7-12 years of age and all will be engaged in a discussion of the study procedures and intervention and risks and potential benefits. Assent forms written in appropriate language for children will be reviewed with children and their mothers/primary caregivers and ample time will be provided to discuss the study procedures, intervention, risks and potential benefits. Written documentation of assent is required prior to starting the study.

Participant Confidentiality

Following HIPAA guidelines, a participant's privacy and confidentiality will be respected throughout the study. Each participant will be assigned a sequential identification number and these numbers rather than names will be used to collect, store, and report participant information. Data reported in medical journals or scientific meetings will be presented in aggregate for participants as a whole. No individual participant will be identified in any way.

The study protocol, documentation, data and all other information generated will be held in strict confidence. No information concerning the study or the data will be released to any unauthorized third party, without prior written approval of the principal investigator at CDC.

Reporting results to study participants

Overview

Results will be given to the study participants for their individual housing unit and clinical tests (when applicable). There are no government standards for residential levels for any of the environmental agents that we are measuring in the study homes. However, during the participants' final home visit, we will: 1) give them the first environmental results that we collected from their home; 2) give them the first clinical results (blood and urine tests) that we collected from the enrolled child; 3) discuss the results with the study participants; and 4) give them information (e.g. local health department phone numbers and a DVD and/or pamphlets) on how to lower environmental agents in their homes. The rest of their results will be mailed to them within one year after they finish the study. The property managers will receive a general report on their complex (not individual unit results). Also, we will consult with building management about appropriate methods of reducing exposures.

Site Monitoring

Site monitoring will occur under the supervision of the CDC PI, [name]. Schedule CDC staff will conduct site visits according to the following schedule:

- Prior to enrollment of the first study participant to ensure that all equipment is in place, and that space and staffing are appropriate.
- After the first 2 study participants have completed the 6-month home visits.
- Subsequently, annually.

- If issues or concerns arise, an ad hoc site visit will be scheduled at the discretion of the CDC.

Procedure

CDC staff will review a random sample of participant charts (de-identified) at each site visit to ensure appropriate completion of all case report forms, and adherence to regulatory policies. A written report of the findings from the site visit will be provided to the site and CDC PI.

Safety Monitoring

The CDC IRB will review any event as requested by the Investigators or CDC.

They will review the study annually, including accrual and adverse events (AE). The CDC IRB will review accrual and adverse events annually.

Safety parameters

Safety parameters will include clinical observation and administration of an unstructured questionnaire of the study participant and mother (if applicable) regarding any events during the course of enrollment in the study. Clinical observation will occur at each of the clinic visits and unstructured questioning will occur at each of the clinic visits.

Definition of Adverse Events and Serious Adverse Events

An adverse event (AE) is any occurrence or worsening of an undesirable or unintended sign (including a clinically significant abnormal laboratory finding), symptom, or disease in a study participant, whether or not it is considered to be study-related. Any worsening of a pre-existing condition or illness is considered an adverse event. An adverse event is considered unexpected when its nature or severity is not consistent with the descriptions in the protocol or consent form.

A serious adverse event (SAE) is defined as any adverse therapy experience occurring at any dose that suggests a significant hazard, contraindication, side effect, or precaution. This includes, but may not be limited to, any of the following events:

1. Death: A death occurring during the study or which comes to the attention of the investigator during the protocol-defined follow-up after the completion of the therapy, whether or not considered intervention-related, must be reported.
2. Life-threatening: Any adverse therapy experience that places the subject or subjects, in the view of the investigator, at immediate risk of death from the reaction as it occurred (i.e., it does not include a reaction that had it occurred in a more serious form, might have caused death).
3. Inpatient hospitalizations or prolongation of existing hospitalization.
4. Persistent or significant disability or incapacity
5. An event that required intervention to prevent permanent impairment or damage.

Assessment of AEs

At every point of contact with the study participant (home visits, clinic visits, and telephone calls, study participants will be asked in an unstructured manner whether they have had any problems since their last study visit. All reportable AEs will be followed until satisfactory resolution or until the PI or sub-investigator deems the event to be chronic or the participant to be stable. All serious adverse events will be followed through resolution by a study physician and reviewed by a study physician.

Adverse events may be discovered through any of these methods:

